#### **2.4.7.3 *Vital signs***

Vital signs will include heart rate (HR, beats/minute), systolic and diastolic blood pressure (SBP/DBP, mmHg), respiratory rate and body temperature (°F or °C). Each vital sign parameter will be summarized as observed parameter value and change from baseline at each scheduled time point.

PCSA values during the study (from first infusion start to last available observation) will be summarized.

#### **2.4.7.4 *Electrocardiogram***

For ECG parameters, the observed data and change from baseline will be summarized at each scheduled time point.

PCSA values will be summarized during the study (from first infusion start to last available observation).

#### **2.4.7.5 *Echocardiogram with Doppler***

Shift tables will be created for valve characterization (including aortic regurgitation, mitral regurgitation, pulmonic regurgitation, tricuspid regurgitation). Summary of change from baseline in ejection fraction (%) and pulmonary artery systolic pressure will be provided. By-patient plots of left ventricular calculated ejection fraction (%) will be provided.

#### **2.4.7.6 *Physical examinations***

Complete physical examination (except overall neurological exam - please see [Section 2.4.7.7](#)) will be classified as normal or abnormal. Shift tables will be provided. A listing of the abbreviated physical examination data will be provided.

Observed values and change from baseline for weight, height and BMI will be summarized for all scheduled time points.

For patients from the pediatric study DFI1303, the age-appropriate growth in height is a matter of efficacy; please see [Section 2.4.8.14](#) for analysis of height z-scores.

#### **2.4.7.7 *Extended neurological examinations***

This data will be summarized and listed. The overall evaluation of neurological exam collected in eCRF under physical exam will be included in this section.

#### **2.4.7.8 *Liver biopsy (Patients from adult study DFI13412)***

Liver biopsy data will be received as external data.

The fibrosis stage will be summarized with number of patients and percentage for each stage at each visit. Cirrhosis and liver failure could be interpreted from this data. Change from baseline in Sphingomyelin from Liver biopsy will be summarized under pharmacodynamics ([Section 2.4.9.1](#)). Any other data from liver biopsies in the clinical database will be provided in a data listing.

#### **2.4.7.9 *Liver ultrasound Doppler (Patients from pediatric study DFI13803)***

Liver ultrasound Doppler data will be provided in a data listing.

#### **2.4.7.10 *Safety biomarkers***

Observed values and change from baseline will be summarized at each scheduled time point. Summary plots for observed values and/or by-patient plots over time will also be presented as appropriate.

#### **2.4.7.11 *Immune response assessments***

Data listings will be provided to display results of anti-olipudase IgG antibody, neutralizing antibody, anti-olipudase alfa IgE antibody, serum tryptase activity, complement activation, and skin testing performed. If IgG antibody titer value is reported as <xx, the numeric value will be imputed as xx, the minimum required dilution (MRD), and used for summary purposes. Listing will provide results as reported as well as results as imputed.

A patient with at least one anti-drug antibody (ADA) response available in the database is considered evaluable.

A patient whose ADA status is positive at baseline is considered to have pre-existing ADA.

A patient whose ADA status is positive anytime post-baseline and is negative or missing at baseline is considered to have treatment-induced ADA.

A patient whose ADA status is positive at baseline (pre-existing ADA) and the ADA titer level anytime post-baseline is significantly higher than that at baseline is considered to have treatment-boosted ADA. A difference in titer values between 2 samples representing greater than or equal to twice the dilution level is considered significant. In other words, the post-baseline titer value divided by the baseline titer value will be greater than or equal to 4 to be considered significant. For example, if baseline titer value is 50, the post-baseline titer value has to be  $\geq 200$ .

For patients with treatment-induced ADA, the following 3 ADA responses are defined.

**Transient ADA response** is defined as:

- Treatment-induced ADA detected only at one sampling time point post-baseline (excluding the last sampling time point).
- Treatment-induced ADA detected at two or more sampling time points post-baseline, where the first and the last ADA-positive samples (irrespective of any negative samples in between) are separated by a period of less than 16 weeks, and the subject's last sampling time point is ADA-negative.

**Persistent ADA response** is defined as:

- Treatment-induced ADA detected at two or more sampling time points post-baseline, where the first and the last ADA-positive on-treatment sample (irrespective of any negative samples in between) are separated by at least 16 weeks.
- Treatment-induced ADA detected in the last two sampling time points, irrespective of the time period in between.

The following subclassifications for persistent ADA response will be considered as well. Since this study is ongoing, the final assessment will be the final assessment at the time of data cutoff date for initial BLA submission.

- Low response - if a patient's peak titer  $\leq 400$  and positive at final assessment. This represents the first titer that is greater than a 4-fold increase from the assay minimum required dilution (MRD). Titers within this range would be considered as Low response.
- Intermediate response - if a patient had persistent ADA response but peak titer is  $>400$  and positive at final assessment.
- Tolerized - if a patient had persistent ADA response, but negative at the final assessment.

**Indeterminate ADA response** is defined as:

- Only the last sampling time point is positive and all previous samples are negative.

Pre-existing ADA =  $100 * (\text{Number of patients with pre-existing ADA at baseline}) / \text{number of evaluable patients}$

ADA Incidence =  $100 * (\text{treatment-boosted} + \text{treatment-induced ADA positive patients}) / \text{number of evaluable patients}$

The following information will be provided:

- Number of ADA evaluable patients
- Number (%) of patients with ADA positive/negative at baseline

- Number (%) of patients that never develop ADA at any time (ie, ADA is always negative during baseline and post-baseline visits)
- Number (%) of patients with treatment-boosted ADA
- Number (%) of patients with treatment-induced ADA
- Treatment emergent ADA: Number (%) of patients with treatment-boosted/treatment-induced ADA
- Duration of ADA response: Number (%) of patients with transient/persistent/indeterminate ADA response (each category separately)
- Number (%) of patients within persistent ADA response subclassifications: low response, intermediate response, tolerized (each category separately)
- Patients with treatment-induced ADA will be further characterized
  - Peak ADA titer: Median and 25th/75th quantiles (min, max) of the ADA titer for peak ADA titer of treatment-induced ADA positive patients
  - Last ADA titer (final assessment): Median and 25th/75th quantiles (min, max) of the last ADA titer of treatment induced ADA positive patients
- Number (%) of patients with positive neutralizing antibody (NAb)
  - NAb Inhibition of catalytic activity
  - NAb inhibition of cellular uptake

The assessment of ADA incidence and characterization by manufacturing process B compared with Process C will be conducted through pooled analyses and presented in the integrated summary of immunogenicity. The assessment of immunogenicity and safety by Processes will be presented in the integrated summary of safety (ISS).

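### SAP 2.4.7.11 labels a persistent-ADA patient tolerized on one negative final sample, so assay fluctuation near the cut-off can produce the label with no change in antibody

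*SAP*

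**What the plan says.** All the rules are in SAP 2.4.7.11 (Immune response assessments).

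- **Persistent, first route.** Two or more positive post-baseline samples are needed, where "the first and the last ADA-positive on-treatment sample (irrespective of any negative samples in between) are separated by at least 16 weeks".
- **Persistent, second route.** "Treatment-induced ADA detected in the last two sampling time points, irrespective of the time period in between".
- **Subclasses of persistent.** Low means a peak titer of 400 or less and positive at the final assessment. Intermediate means a peak above 400 and positive at the final assessment. The third is "Tolerized - if a patient had persistent ADA response, but negative at the final assessment".
- **Which sample is final.** "Since this study is ongoing, the final assessment will be the final assessment at the time of data cutoff date for initial BLA submission".
- **Indeterminate.** Only the last sample is positive and every earlier one is negative.
- **Treatment-boosted.** "A difference in titer values between 2 samples representing greater than or equal to twice the dilution level is considered significant"; the SAP restates this as a ratio of at least 4.
- **Titers reported as below a limit.** They are set equal to that limit, the minimum required dilution (MRD).

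The number and percentage of patients in each subclass is a planned output of the same section. IgG is sampled about quarterly (SAP 2.1.3.3), and monthly for six months after a manufacturing process switch (protocol flow charts, Section 1).

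**The concern.** Persistence and tolerization are read from the same positive/negative status. The persistence rule accepts that a persistent patient may test negative now and then, because it disregards negatives lying between positives. If the same isolated negative falls on the last sample before the cutoff, it is reported as loss of antibody.

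The section is more careful elsewhere. A lone positive at the end is not treated as an established response, and a titer rise counts only at four-fold or more. Tolerization has no such protection: no second negative, no minimum time negative, no required fall in titer. For a patient whose antibody has not changed, the error runs only towards the more reassuring label. The final sample is set by an administrative cutoff, so no later sample corrects the label in that analysis.

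**Working it through.** **1. The SAP's own figures.** The four-fold example is 50 × 4 = 200, as stated. The low-response ceiling is described as the first titer more than four-fold above the MRD. In the doubling series 50, 100, 200, 400, the first value above 4 × 50 = 200 is 400, which agrees if the MRD is 50. That is an inference, since 50 appears only as an example baseline titer.

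**2. How the section treats one isolated reading.**

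| Reading | Treatment in SAP 2.4.7.11 |
|---|---|
| One negative between positives | ignored |
| One positive, last sample only | indeterminate |
| Titer rise below four-fold | not boosted |
| One negative, last sample, in a persistent patient | tolerized |

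The second persistence route needs the last two samples positive, so every tolerized patient comes through the first route.

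**3. Chance of the label with unchanged antibody.** Let q be the probability that one sample from a truly positive patient reads negative, with errors independent between samples. Once earlier samples have established persistence:

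- current rule: P(tolerized | persistent) = q
- last two samples negative: P ≈ q²

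A simulation applying the SAP rules literally (400,000 patients per setting; 8, 12 or 20 samples 13 weeks apart) agrees. Miss rates of 5%, 10% and 20% gave tolerized shares of 5%, 10% and 20%, and 0.25%, 1.0% and 4.0% with two negatives. The share dropped visibly below q only with 8 samples and very high miss rates (47% for q = 50%).

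**4. Illustrative q by true titer.** Assumptions, none of them in the documents: cut-off at titer 50, normal assay error on the log2 scale, and a negative reading when the result is more than half a dilution below 50. For a true titer of 50 × 2^k, q = Φ((−0.5 − k)/SD).

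| True titer | SD 1 dilution | SD 0.5 dilution |
|---|---|---|
| 50 | Φ(−0.5) = 30.9% | Φ(−1) = 15.9% |
| 100 | Φ(−1.5) = 6.7% | Φ(−3) = 0.1% |
| 200 | Φ(−2.5) = 0.6% | about 0 |
| 400 | Φ(−3.5) = 0.02% | about 0 |
| Equal mix, mean of q | 9.5% | 4.0% |
| Equal mix, mean of q² | 2.5% | 0.6% |

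The last row averages q² over titers. Squaring the average would give 0.9% for SD 1, which is too low because the risk is concentrated at titer 50.

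**5. Higher titers.** If half of persistent patients had current titers well above 400, where q is close to zero, the current-rule figures would halve: 9.5%/2 = 4.8% and 4.0%/2 = 2.0%.

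**6. In patients.** Take 10 persistent patients (assumed) and q = 10%. The expected number of spurious labels is 10 × 0.10 = 1.0, and P(at least one) = 1 − 0.90^10 = 65%. With two negatives these are 10 × 0.01 = 0.1 and 1 − 0.99^10 = 10%.

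**7. Timing.** Nominal pediatric visits at weeks 14, 26, 38, 52, 66, 80, 92, 104 are 12 or 14 weeks apart. One quarterly negative falls 12 to 14 weeks after the last positive, and the second falls 24 to 28 weeks after it. Under monthly sampling, two negatives span only about two months from the last positive.

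**The case against.** The best defense is that little depends on this label. Tolerized is a subclass of persistent, so the patient stays in the persistent, treatment-induced, treatment-emergent and ADA-incidence counts and in the peak-titer summary. Last titers are summarized and IgG results are listed, so a lone final negative can be found. Safety summaries are descriptive, with no formal testing (protocol 11.6.3). The efficacy subgroups in SAP 2.4.8.15 use treatment-emergent ADA status, not tolerization. All of this stands and confines the point to one split. It does not correct a percentage printed in a summary table.

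Four stronger readings are tempting, and the documents do not support them.

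- *Fluctuation will create tolerized patients, at 9.5%.* The documents give no assay precision, no titer distribution, no stated MRD and no rule linking status to titer. They support *can*, and the percentage is illustrative.
- *Continuing antibody is understated overall.* Only the subclass changes; the counts listed above do not.
- *The patients moved are those in low response.* Low and intermediate are split on peak titer, whereas a chance negative depends on current titer. A patient with a past peak above 400 and a low titer now would leave intermediate.
- *A primary endpoint is compromised.* Immune response assessments are one item in the protocol's list of primary safety endpoints (9.1.1), and protocol 11.6.3.3 asks for presence, absence and titers. The tolerized split is an SAP addition.

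**Conclusion.** The point holds as a defect in one definition. A single final negative suffices for tolerized, in a section that otherwise does not rely on single readings, and it gives an unchanged patient that label with probability q. Under the assumed equal spread of true titers over 50 to 400, that is about 4% to 9.5% of persistent patients for an assay SD of 0.5 to 1 dilution, and less if current titers are higher. The risk lies mainly in patients within about one dilution of the cut-off.

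The reduction to about q squared assumes independent errors between samples. The effect is limited to the descriptive low/intermediate/tolerized table. With about 25 patients expected (SAP 1.1; SAP 1.3 says 17), one spurious label still moves a percentage visibly: 10 points if 10 patients are persistent. The definition should be changed, but no primary conclusion depends on it.

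**What to change.** Define tolerized as persistent ADA with at least the last two consecutive samples negative and the final negative at least 16 weeks after the last positive. Two quarterly negatives meet this. Two closely spaced monthly negatives after a process switch do not. The 16 weeks should run from the last positive: requiring the negatives themselves to be 16 weeks apart would take three nominal quarterly samples.

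Report persistent patients who are negative at the final assessment but do not meet this rule on a separate line, for example *persistent, last sample negative, unconfirmed*. The low and intermediate definitions, which require a positive final assessment, can then stay as they are.

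The cost is a short SAP edit, one extra table row and a small programming change, using samples already planned. The downside is that a patient who truly lost antibody shortly before the cutoff is shown as unconfirmed rather than tolerized.

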#### **2.4.8 Analyses of efficacy endpoints**

All efficacy analyses to assess changes in organomegaly (spleen and liver), infiltrative lung disease, pulmonary function, cycle ergometry endpoints, physician's global assessment, hemoglobin/platelet, efficacy biomarkers, lipid profile, bone biomarkers, health outcome questionnaires, will be performed using the safety population. Additional endpoints for pediatric patients include: linear growth (height z-score), bone age, tanner staging and cognitive and adaptive functioning (up to the age of 6 years only).

Baseline for efficacy parameters will be defined as the last non-missing value before the first infusion in the original study, except for hemoglobin and platelet; for complete definition of baseline values, please refer to [Section 2.6.1](#).

#### **2.4.8.1 *Spleen and liver volumes***

For timing of MRI measuring spleen and liver volume, and the formula for calculating the volumes in multiples of normal (MN), refer to [Section 2.1.4.1](#).

Change from baseline and percent change from baseline for both  $\text{cm}^3$  and MN units, in addition to observed values, will be calculated and summarized for all scheduled visits. The analysis of covariance method (including baseline as covariate) and Wilcoxon-Mann-Whitney (WMW) test p-values (and 95% confidence interval) for the change from baseline and percent change from baseline will be provided in the summary tables for spleen/liver volumes in MN unit. Box plots of observed values for spleen and liver volumes in MN unit will be provided.

The correlation between spleen and liver volumes with other efficacy/safety/pharmacodynamic parameters may be explored graphically.

Analysis of covariance will be used to explore difference among different age cohorts for patients from pediatric study DFI13803, using the following model:

Percent change from baseline = age cohort + baseline

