8.2 BLINDING PROCEDURES

Not applicable. This is a single-arm, open-label study design.

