11.6.2 Analyses of efficacy endpoints

Efficacy assessments are described in [Section 9.2](#).

Summary statistics for the values, nominal change from baseline, and percent change from baseline will be presented for efficacy assessments at various study time points. The baseline value is defined to be the latest assessment value prior to the first dose of study treatment in the primary study. For selected parameters, the mean (95% confidence interval) or median (interquartile range) may be plotted over time. Categorical variables will be summarized using frequencies and percentages at various study time points.

The association between changes in efficacy parameters and total amount of drug received may be examined.

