## LIST OF ABBREVIATIONS AND DEFINITION OF TERMS

ABAS-3:	Adaptive Behavior Assessment System, Third Edition
ADA:	anti-drug antibody
AESI:	adverse events of special interest
AP:	alkaline phosphatase
AUC 0-inf :	area under the concentration versus time curve from time 0 to infinity
BMI:	body mass index
CL:	total body clearance
C max :	maximum plasma concentration
CV:	coefficient of variation
DBP:	diastolic blood pressure
DBS:	dried blood spots
DP-3:	Developmental Profile 3
DXA:	dual-energy X-ray absorption
ECG:	electrocardiogram
e-CRF:	electronic case report form
FEV 1 :	forced expiratory volume in the first 1 second
FVC:	forced vital capacity
HDL:	high-density lipoprotein
HR:	heart rate
LDL:	low-density lipoprotein
LLOQ:	lower limit of quantification
NE:	not evaluable
PCSA:	potentially clinically significant abnormality
PKDM:	pharmacokinetics, dynamics and metabolism
PT:	preferred term
SAE:	serious adverse event
SAP:	statistical analysis plan
SBP:	systolic blood pressure
SD:	standard deviation
SEM:	standard error of the mean
SMPD1:	acid sphingomyelinase gene
SOC:	system organ class
t 1/2z :	terminal half-life
t max :	time to reach C max
ULN:	upper limit of normal
VAS:	visual analogue scale
VLDL:	very low-density lipoprotein
V ss :	volume of distribution at steady state.
WHO-DRUG:	World Health Organization-Drug Dictionary
WMW:	Wilcoxon-Mann-Whitney

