#### **2.1.4.2 Pulmonary function tests**

Pulmonary function tests (PFT) will be performed in patients  $\geq 5$  years old at screening in the original study to measure lung volumes, air flow, and gas exchange for evidence of interstitial lung disease (ILD) at approximately every 6 months for first 2 years in this study (starting at 3 months in this study for pediatric patients), and every 12 months thereafter; for further details of timing, please refer to the protocol. Completion of PFTs may depend on patient age or cooperation, or both.

Pulmonary function testing will include, but will not be limited to, assessment of forced vital capacity (FVC), forced expiratory volume in the first 1 second (FEV1) of the FVC maneuver, and total lung capacity. Diffusing capacity of carbon monoxide (DLCO) will be used to measure gas exchange across the alveolocapillary membrane. Observed values of PFT parameters and DLCO will be reported. Percent predicted values will be computed based on following algorithm (height and hemoglobin values are from the available ones closest to the PFT evaluation date/time, and age is calculated at the PFT evaluation date):

Percent predicted values of FEV1 and FVC will use the Global Lung Initiative (GLI) 2012 reference equations (1).

Predicted TLC (Liters) will use the following formula for adults (2) and children (3)

Adults ( $\geq 18$  years of age):  $= 0.0795 * \text{height(cm)} + 0.0032 * \text{Age(years)} - 7.333$  for males  
 $= 0.0590 * \text{height(cm)} - 4.537$  for females

Children ( $< 18$  years of age):  $\exp(24.67 - 4.91 * \ln(\text{Height(cm)}) - 7.16 * \ln(\text{Age(months)}) + 0.059 * \text{Sex} + 1.47 * \ln(\text{Height}) * \ln(\text{Age}))$

Percent predicted TLC =  $100 * \text{Observed TLC} / \text{Predicted TLC}$

Percent predicted DLCO will be computed as follows: (2, 4) and children (3, 4):

Predicted DLCO (adults), mL CO/min/mmHg:  
 $= 0.416 * \text{Height(cm)} - 0.219 * \text{Age(years)} - 26.34$  for males  
 $= 0.256 * \text{Height(cm)} - 0.144 * \text{Age(years)} - 8.36$  for females

Predicted DLCO (children), mmol/min/kPa (Sex: 0=female, 1=male):  
 $= \exp(34.80 - 6.89 * \ln(\text{Height(cm)}) - 8.66 * \ln(\text{Age(months)}) + 0.10 * \text{Sex} + 1.79 * \ln(\text{Height}) * \ln(\text{Age}))$

Unit conversion: mL CO/min/mmHg = mmol/min/kPa \* 2.987

Hb-adjustment factor (to be applied to DLco in unit of mL CO/min/mmHg)  

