## **2.4 STATISTICAL METHODS**

Data collected in this study will be presented using summary tables, figures, and data listings. Descriptive statistics for categorical variables will be provided using frequencies (n) and percentages (%). Descriptive statistics for continuous variables will be provided using number of observations (n), mean, standard deviation (SD), median, minimum, and maximum. All data used in tabular summaries or figures will be supported by listings of underlying data – raw and/or derived, and all figures will be supported by relevant summary information.

All summaries will be provided for the LTS population, along with separate subgroups in the population according to which original study the patient belonged to: DFI13412 (adult study, Phase 1B, 26 weeks, 5 patients), DFI13803 (pediatric study, Phase 1/2, 64 weeks, 12 patients). In addition, similar summaries will be produced by age cohort of adolescent, child, infant for the patients who transition from pediatric study DFI13803.

The scheduled visits in statistical displays will be labelled in months of total follow up time from the first infusion in the original study. For example, a 6-month visit in this study for a patient transitioning from the 26-week DFI13412 study will be identified as Month 12 exposure in the displays. The schedule of measurements for this study will be followed for display presentation with baseline derived from the original study. For patients in this study, the results from the original study visits will be included, unless specified otherwise, for the purpose of understanding the continuity of treatment effect during this extension phase; for details and descriptions of all results from the original study, please refer to the original study CSR. For parameters that are not collected in the extension phase will not be part of this SAP.

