#### **2.4.8.2 *Pulmonary function testing***

The parameters evaluated are DLco (mL/min/mmHg), FVC (L), FEV1(L), TLC (L). Since the local sites use different equations to calculate percent predicted values, the calculation is standardized internally by using the formula provided in [Section 2.1.4.2](#); the percent predicted values calculated at site will remain in the database but will neither be listed nor summarized. The observed values used in analyses are provided by local sites for original study, and will be used for calculation of percent predicted values. The patients transitioning from the pediatric study will continue to use children formula used during the original study even if the age limit prescribed for that formula is crossed during the extension phase.

For all 4 tests, percent (%) predicted values will be summarized for observed values, change from baseline and percent change from baseline using the safety population at scheduled study visit. The analysis of covariance method (including baseline as covariate) and WMW test p-values for the change from baseline and percent change from baseline will be provided in the summary tables for all 4 tests. Box plots of observed values, percent change from baseline for these 4 tests will be provided for the safety population. By-patient plots for all 4 tests over time will be provided.

Analysis of covariance will be used to explore difference among different age cohorts for patients from pediatric study DFI13803, using the following model:

Percent change in percent predicted PFT from baseline = age cohort + baseline percent predicted PFT

For patients from adult study DFI13412, a binary measure of responder (yes vs no) will be derived based on the change from baseline in % predicted DLco at each post-baseline visit. A patient is a responder at the visit, if the patient has change from baseline in % predicted DLco  $\geq 15$ . This binary measure of % predicted DLco will be included in data listing.

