### 2.6.2 Missing data

In general, no imputation is planned for missing data. The following approaches are default methods for missing data handling. Some exploratory analyses can be planned with different strategies for treating missing outcomes.

- Categorical data at baseline will be summarized for each age group cohort using counts (n) and percentages (%). The number of patients with missing data may be mentioned, but will not be included in the denominator for the calculation of percentages unless otherwise specified. When relevant, the number of patients with missing data is presented.

- Continuous data: The analyses and summaries for variables with continuous scales will be based on observed data only.

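### SAP 2.4.8.1 and 2.4.8.2 name a two-sample rank test for within-patient change in a single-arm study, with no second sample and no rule for groups of five or fewer

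*SAP*

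**What the plan says.** SAP 2.4.8.1 specifies, for spleen and liver volumes in multiples of normal, an ANCOVA with baseline as covariate and "Wilcoxon-Mann-Whitney (WMW) test p-values (and 95% confidence interval) for the change from baseline and percent change from baseline will be provided". SAP 2.4.8.2 specifies an ANCOVA and "WMW test p-values for the change from baseline and percent change from baseline will be provided in the summary tables for all 4 tests"; it mentions no interval. The SAP's abbreviation list expands WMW as "Wilcoxon-Mann-Whitney".

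Protocol 8.2 describes the design: "This is a single-arm, open-label study design". Both SAP sections then assign differences among pediatric age cohorts to a separate ANCOVA with age cohort and baseline as terms.

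SAP 2.4 requires summaries overall and by original study, with five adults from DFI13412. It adds that "similar summaries will be produced by age cohort of adolescent, child, infant for the patients who transition from pediatric study DFI13803". SAP 2.6.2 states: "The analyses and summaries for variables with continuous scales will be based on observed data only". Under SAP 2.1.4.2, pulmonary function tests are limited to patients who were at least 5 "years old at screening in the original study to measure lung volumes".

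Protocol 11.6.2 plans description for efficacy: "Summary statistics for the values, nominal change from baseline, and percent change from baseline will be presented for efficacy assessments". Protocol 11.6.2.1 treats multiplicity as not applicable.

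**The concern.** The named test needs two independent groups, but the quantity to be tested is one column of within-patient changes. A programmer cannot produce the p-value without supplying something the SAP does not contain: a second sample, or a different test.

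Two smaller gaps follow. In 2.4.8.1 the wording leaves open whether the 95% interval belongs to the ANCOVA or to the rank test. And once a one-sample rank test is substituted, the plan to report by original study and age cohort produces groups in which that test cannot give a 95% interval or a p-value below 0.05, with no instruction on what to print.

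At stake are the rank p-values for spleen volume, liver volume and four pulmonary function measures in the visit tables.

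**Working it through.** The documents give no alpha, power or derived sample size for this test, so there is no figure of the plan's own to reproduce. A two-sided 0.05 level is assumed below, to match the 95% interval.

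**Step 1: is there a second sample?** The candidates are:

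- A control arm: none (Protocol 8.2).
- Age cohorts: three groups, and assigned to ANCOVA in the same two sections.
- Severity and antibody subgroups (SAP 2.4.8.15): ANCOVA within each subgroup.
- Adults versus pediatric patients: not mentioned, and it would test a difference between source studies, not change from baseline.

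SAP 1.6 also describes the t-test used earlier as a test of change from baseline. The target is within-patient change, and no second sample is assigned.

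**Step 2: what could a workaround do?** Neither version below appears in the SAP. They show only that the gap is not harmless.

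*Changes against a column of n zeros.* If K of n patients increase, U = n·K. The statistic depends only on K, and under a median change of zero K is Binomial(n, 0.5). The variance corrected for the n tied zeros is (n²/12)·[(2n+1) − (n³−n)/(2n(2n−1))]. Null rejection at nominal 5%:

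| n | Rejects when K is | Probability |
|---|---|---|
| 4 | 0 or 4 | 2·1/16 = 12.5% |
| 5 | 0 or 5 | 2·1/32 = 6.25% |
| 6 | ≤1 or ≥5 | 2·7/64 = 21.9% |
| 12 | ≤3 or ≥9 | 2·299/4096 = 14.6% |
| 20 | ≤6 or ≥14 | 2·60460/1048576 = 11.5% |

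Example with n=12, 3 up and 9 down: U = 36, mean 72, variance 12·(25 − 1716/552) = 262.7, SD 16.2. With continuity correction z = 35.5/16.2 = 2.19, so p is about 0.03. The sign test on the same data gives 2·299/4096 = 0.146.

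*Baseline against visit as unpaired samples.* This is possible for absolute change only; percent change has no such form. Simulated null rejection (bivariate normal, equal variances) at assumed pre/post correlations 0.5 / 0.8 / 0.95:

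| n | Rejects |
|---|---|
| 5 | 0.8 / 0.1 / 0.0% |
| 12 | 0.9 / 0.1 / 0.0% |
| 20 | 0.8 / 0.0 / 0.0% |

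With five assumed baselines of 6, 9, 12, 16 and 22 multiples of normal, a uniform 25% fall gives an unpaired p of 0.548, and a uniform 80% fall gives 2/C(10,5) = 2/252 = 0.0079. The exact signed-rank p is 0.0625 in both cases. The workaround can mislead in either direction.

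**Step 3: what can the one-sample test deliver in small groups?** The smallest exact two-sided signed-rank p is 2/2ⁿ, and the largest exact interval coverage is 1 − 2/2ⁿ.

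| n | Smallest p | Largest coverage |
|---|---|---|
| 3 | 0.25 | 75% |
| 4 | 0.125 | 87.5% |
| 5 | 0.0625 | 93.75% |
| 6 | 0.03125 | 96.9% |

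Six is the smallest n that allows either p<0.05 or a 95% rank interval. The choice of exact or asymptotic calculation also matters: at n=5 with all changes in one direction, the normal approximation gives 0.043 without and 0.059 with continuity correction, against 0.0625 exact. The SAP does not say which is used.

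**Step 4: which groups are that small?**

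- Adults: never more than 5.
- Pediatric cohorts with 12 patients (SAP 1.3 and 2.4): 12/3 = 4, so at least one cohort has 4 or fewer.
- Pediatric cohorts with about 20 (SAP 1.1, Protocol 6): 20/3 = 6.7, so the smallest has 6 or fewer. A group of 5 or fewer is then possible but not guaranteed.

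Missing visits and the age limit for pulmonary function tests can lower n further. The whole pediatric group (12 or about 20) and the pooled population (17 or about 25) are above the limit at those counts.

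**The case against.** The strongest reply is that this is a misnomer. In context the signed-rank test is the natural reading, an experienced programmer would use it, and then no result changes. That is plausible and keeps the point small, but it concedes that the test named is not the test meant. The SAP exists to fix that choice in advance.

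It is also fair that the error rates in Step 2 describe programming choices found nowhere in the documents. A reader might infer that the reported p-values will be badly inflated or nearly powerless. The documents do not support that: taken literally the test cannot be run at all, and the rates belong to hypothetical repairs.

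A reader might infer that many reporting groups will have five or fewer patients. Only the adult group is certain, plus one age cohort if 12 pediatric patients enrol. The documents give no cohort sizes.

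A reader might also extend the criticism to the baseline-only ANCOVA that replaced the paired t-test, or to the reason SAP 1.6 gives for it. That is a modelling preference: baseline adjustment is defensible, and nothing in the documents makes it an error.

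Finally, the limit at five patients is a property of any exact one-sample rank test, not a fault in the SAP's text. It is raised because the correction needs a rule for it.

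**Conclusion.** The error is real and confined to two sections. A two-independent-sample test is prescribed for one-sample data, no second sample is named, and the 95% interval in 2.4.8.1 has no clear owner. This rests on the text alone. The limit of five patients is exact, given the assumed two-sided 0.05 level and 95% coverage.

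The consequence is modest. Efficacy is secondary, the protocol plans descriptive summaries, there is no multiplicity scheme, and no decision depends on these p-values. It would be wrong to conclude that the efficacy findings are unsound: observed values and changes are tabulated whichever test is used. The point is worth correcting because the p-values are planned for summary tables, and as written their calculation is left to an unrecorded choice.

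**What to change.** In SAP 2.4.8.1 and 2.4.8.2:

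- Replace WMW by the exact one-sample Wilcoxon signed-rank test on change and percent change, with a Hodges-Lehmann interval where an interval is given. If a between-group comparison was meant, name the two groups.
- Where five or fewer patients are observed at a visit, do not label the rank interval 95%. Either report its attainable level (93.75% at n=5, 87.5% at n=4) with a footnote giving the smallest possible p (0.0625, 0.125), or give descriptive values only.
- State which method the 95% interval in 2.4.8.1 belongs to.
- Label the p-values exploratory.

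The age-cohort and baseline-adjusted ANCOVAs can stay as they are. The cost is a few sentences and a change of one procedure in the code. The downside is that groups of five or fewer cannot reach a rank p-value below 0.05.
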